8.3.4. Handling of Missing Data

Patients with missing data due to death will be assigned the worst possible outcome, where applicable. Patients who do not complete D14 assessment and have study discontinuation for lack of efficacy, non-compliance with study drug, progressive disease, lost to follow-up, or adverse event will have primary endpoint response imputed as PRI. If study discontinuation reason was recovery, the primary endpoint will be imputed as no PRI. Other strategies for handling missing data will be described in the SAP.

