#### 16.2.3.3. Duration of Hospitalization for COVID-19 (days)

A secondary endpoint is the duration of hospitalization/confinement in days, defined as the time from start of treatment to either achieving Status 7 or 8 on the NIAID Clinical Status scale or hospital discharge (which ever happens first). Data from the follow-up period after Day 14 will be included. This endpoint will be calculated as follows:

- Duration of Hospitalization for COVID-19 (days) = ((Date of achieving status 7 or 8 OR hospital discharge) – Study Day 1) +1

Subjects who don't achieve status 7 or 8 nor have hospital discharge will be censored at end of study (EOS).

Subjects who die will be censored to the latest EOS date available.

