#### 16.2.3.4. Time to Sustained Non-detectable SARS-CoV-2 (days)

A secondary endpoint is the time to sustained nondetectable SARS-CoV-2 RNA from randomization in days,

Document: \\[REDACTED]\net\enterprise\Apps\sasdata\SASb\SAS\Atea\_Pharmaceuticals\AT-527\SAZ\A63631\Biostatistics\Documentation\SAP\AT-03A-001\_V1.0\_COVID\_SAP\_PA7.doc

[figure not shown]
Author: [REDACTED] Version Number: V1.0  
Version Date: 15Apr2021

Template No.: CS\_TP\_BS016 Revision 6

Reference: CS\_WI\_BS005

Effective Date: 02Dec2019

Copyright © 2009, 2010, 2012, 2016, 2018, 2019 [REDACTED] All rights reserved. The contents of this document are confidential and proprietary to [REDACTED] Holdings Inc. and its subsidiaries. Unauthorized use, disclosure or reproduction is strictly prohibited.

calculated as follows:

- Time to sustained nondetectable SARS-CoV-2 (days) = (Start date of sustained nondetectable SARS-CoV-2 – Date of randomization) +1

The SARS-CoV-2 test results during the study will be captured by the Central Laboratory. The start date of sustained nondetectable SARS-CoV-2 is defined as the earliest date when the test result is negative and remains negative until end of the study or D14 as the test is not required after that day.

Analysis of this endpoint will be performed on the mITT analysis set only. Both COBAS and TaqPath assays report results as detectable or non-detectable. Each method has its own limit of detection. The analyses will be performed separately on results from each assay.

The following algorithm will be followed to determine how a subject which didn't meet the event (i.e., Non-detectable SARS-CoV-2) should be censored:

1. If the subject has no post-baseline SARS-CoV-2 test results, the subject will be censored at the date of first dose of study drug;
2. If the subject's SARS-CoV-2 test remain positive during the study, the subject will be censored at the date of their latest of SARS-CoV-2 test with a non-missing result;
3. If the subject has negative SARS-CoV-2 but not sustained, i.e. the negative result was not confirmed at a later scheduled visit (due to missing data, early discontinuation, study completion, etc.), the subject will be censored at the date of their latest SARS-CoV-2 test date with a non-missing result;

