#### 16.3.1.2. Time to COVID-19 Symptom Resolution

An exploratory efficacy endpoint is the time to all COVID-19 symptoms resolution from randomization, in days.

The time to symptoms resolution will be calculated as follows:

- Time to symptom resolution (days) = (Latest post-baseline assessment symptom end date – Date of randomization)

Time to symptom resolution will be calculated using data from COVID-19 Symptom Duration page the eCRF.

Subjects will be censored as follows:

1. If the subject has no post-baseline date, the subject will be censored at the date of first dose of study drug;
2. If the subject's symptoms are ongoing, i.e. no end date recorded, the subject will be censored at the subject's end of study date.

If subject has no COVID-19 symptom at baseline, the subject will be censored at Day 1

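### Time to sustained RNA clearance has no rule for death, so an early death is censored at the last test and clearance in that arm is slightly overstated

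*SAP*

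**What the plan says.** **Protocol 8.3.4** sets a general principle: "Patients with missing data due to death will be assigned the worst possible outcome, where applicable". It then adds: "Other strategies for handling missing data will be described in the SAP".

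**SAP 16.2.3.4** (sustained clearance, mITT only) lists five censoring rules, and none mentions death. A subject with no post-baseline test is censored at first dose. For a subject who stays positive the rule reads: "test remain positive during the study, the subject will be censored at the date of their latest of SARS-CoV-2 test". For one with an unconfirmed negative: "the subject will be censored at the date of their latest SARS-CoV-2 test date with a non-missing result".

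**SAP 16.2.3.5** (first negative test) has the same gap: subjects who remain positive are censored at the last test. **SAP 16.2.5** analyses both endpoints by Kaplan-Meier and log-rank, with the p-value labelled descriptive.

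Elsewhere the SAP does make provision for death:
- Duration of hospitalization (16.2.3.3): "Subjects who die will be censored to the latest EOS date available".
- Clinical recovery, Kaplan-Meier sensitivity analysis (16.2.4.2): a death without recovery is censored at Day 15.
- Time to NEWS ≤ 2 (16.3.1.1): a death is censored one day after the largest observed time.
- Proportion positive (16.2.3.6): a missing test counts as positive, with no exception for death.

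**SAP 16.3.1.2** (symptom resolution) has no death rule either: "If the subject's symptoms are ongoing, i.e. no end date recorded, the subject will be censored at the subject's end of study date".

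**The March 2022 changes form** keeps sustained clearance as Table 14.2.5.4, applies the same approach to infectious titer in Table 14.2.5.6, and adds no death rule.

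**The concern.** Kaplan-Meier and log-rank assume that a censored subject has the same future chance of the event as those still at risk. A subject who has died cannot clear afterwards. Censoring at the last positive swab removes that subject from the risk set and in effect gives them the survivors' later clearance rate. The clearance curve of an arm with early deaths then sits higher than it would if those deaths counted as never clearing.

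Nothing in the SAP presents this as a deliberate choice. SAP 7.2 does not list 16.2.3.4 or 16.2.3.5 among the sections that handle missing efficacy data, and SAP 3.3 as published records no departure from protocol 8.3.4. On the same virology data, a subject who has died counts as positive in 16.2.3.6 but leaves the risk set in 16.2.3.4.

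The changes form also drops the all-cause mortality analysis, the death summary and the proportion-positive analysis. Few remaining outputs would let a reader see the effect beside the clearance curve.

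**Working it through.** The plan gives no power, event count or expected clearance for this endpoint, so there is no figure of its own to reproduce. The check is a constructed example.

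**Inputs**
- n = 40 per arm. Part A randomized 81 subjects 1:1 (protocol 3.1), and the changes form says that Part B is listed only.
- Clearance of 47% and 22%: the Day 14 undetectable proportions for AT-527 and placebo in the interim analysis (protocol 1.1). These are point prevalences in the subset with baseline viral load at or above the median. They are not sustained clearance in a full arm and serve only as illustration.
- d, deaths without clearance before the Day 14 test: not given in the documents. Assumed 1 to 8.
- Last test before death: assumed Day 2, 5 or 8.

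**Approximation.** If a proportion p of survivors clear, keeping the d deaths in the denominator gives p(n − d)/n. Removing them gives p. The difference is p × d / n.
- 0.47 × 2 / 40 = 0.0235, about 2.4 points.
- 0.22 × 2 / 40 = 0.011, 1.1 points.

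**Product-limit check.** Take 19 clearances in 40, placed 1, 2, 3, 4 and 9 on Days 5, 8, 10, 12 and 14 (assumed), and 2 deaths.
- Deaths kept at risk past the last event: 19/40 = 47.5%.
- SAP rule, last test Day 2: both deaths leave before the first clearance, so 19/38 = 50.0%.
- SAP rule, last test Day 8: 1 − (37/40) × (19/35) = 49.8%.

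The same calculation over the assumed range, with last tests on Days 2 to 8:

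| Early deaths in 40 | 19 cleared: SAP rule minus 47.5% | 9 cleared: SAP rule minus 22.5% |
|---|---|---|
| 0 | 0 | 0 |
| 1 | 1.1 to 1.2 points | 0.5 to 0.6 points |
| 2 | 2.3 to 2.5 points | 1.1 to 1.2 points |
| 4 | 4.8 to 5.3 points | 2.3 to 2.5 points |
| 8 | 11.0 to 11.9 points | 5.2 to 5.6 points |

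The effect scales with 1/n, and the mITT arms will be smaller than 40. If the 62 subjects evaluable for virology at the interim split evenly (31 per arm), 2 deaths give 0.47 × 2 / 31 = 3.0 points or 0.22 × 2 / 31 = 1.4 points.

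**Treatment contrast.** The bias in the difference is p₁d₁/n − p₀d₀/n, where 1 is AT-527 and 0 is placebo. With 2 deaths in each arm it is (0.47 − 0.22) × 2 / 40 = 1.25 points towards AT-527. With 2 deaths on AT-527 only it is about +2.4 points, and with 2 on placebo only about −1.1 points. With equal deaths and equal clearance it is zero.

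**Where a replacement censoring time must lie.** Time to clearance is the event date minus the randomization date, plus 1 (16.2.3.4). Study Day counts from first dose (6.1). If dosing starts the day after randomization, a Study Day 14 swab has time 15; the changes form had to handle exactly this for clinical recovery. SAP 6.4 (Table B) also maps unscheduled tests on Days 14 to 18 to the Day 14 visit. Events can therefore fall after time 14, and a death censored at Day 14 could leave the risk set before them.

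**The case against.** The strongest reply is that this does not breach the protocol. The worst-outcome rule applies only where applicable, other strategies are left to the SAP, and the protocol's worked imputation rules concern the primary respiratory endpoint. That stands. A reader might infer a flat contradiction of protocol 8.3.4, but the wording supports only an inconsistency with its principle. The inconsistency remains, because the SAP gives death a late censoring time for three other time-to-event endpoints and gives no reason for leaving this one out.

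A second reply is that little depends on it. The p-value is descriptive, only deaths before the Day 14 test matter, and the protocol reports low progression rates. That also stands and limits the weight of the point. Time to first negative test is on the form's list of analyses not presented, so that gap matters only if the analysis is run.

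A reader might extend the point to symptom resolution, taking the end-of-study date of a subject who dies to be the date of death. The documents do not say so. Protocol 5.7 defines the end of study for any individual as the 49-day follow-up visit, and on that reading the subject stays at risk to about Day 63 (14 + 49), which is close to what is wanted. SAP 16.2.3.3 separates a subject's own end of study from the latest available date for those who die, so the death-date reading is plausible but not established. Symptom resolution also falls among the exploratory analyses that the form does not present, although the same form updates its derivation and cites Tables 14.2.4.X. Those entries need reconciling.

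**Conclusion.** The point holds for sustained clearance, and for first negative test if it is run, as a minor gap worth closing. Under the stated rules, a subject who dies before the Day 14 test without clearing is treated as non-informatively censored, and clearance in that arm is overstated relative to counting the death as never clearing. The size is roughly 1 to 2.5 percentage points for 2 early deaths in 40, and zero without early deaths. This rests on an assumed death count and on clearance figures borrowed from the high-viral-load subset.

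It would go too far to say that the comparison always favours the arm with more deaths. The upward direction is certain for each arm's own curve. The contrast is biased only if early deaths or clearance rates differ between arms, and then in either direction. For symptom resolution the documents show an undefined term, not a demonstrated bias.

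**What to change.** 1. For sustained clearance, and for first negative test if it is run, state that a subject who dies without the event is censored beyond the last observed event time on the endpoint's own scale, for example one day after the largest observed time, as for NEWS. Do not use Day 14.
2. The form says that the SAP will not be updated, so record the rule on the changes form or in the footnote of Table 14.2.5.4, and of Table 14.2.5.6, which takes the same approach. Both timing options printed on the form fall after unblinding, so state when the rule was added.
3. If nobody died before the Day 14 test without clearing, a footnote saying so settles both tables.
4. For symptom resolution, state whether the end-of-study date of a subject who dies is the date of death or the scheduled end of study. Reconcile the form's two entries on this endpoint, and apply the same rule if it is presented.

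The cost is one sentence, one line of code and a rerun of the tables concerned. No new data are needed.

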#### 16.2.3.5. Time to first SARS-CoV-2 Negative Test

A secondary endpoint is the time to first SARS-CoV-2 negative test in days, calculated as follows:

- Time to first SARS-CoV-2 negative test (days) = (First negative SARS-CoV-2 Date – Date of randomization) +1

Document: \net\enterprise\Apps\sasdata\SASB\SAS\Atea Pharmaceuticals\AT-

Netcentricprise Apps SASdata SACD SACD Attea\_1 pharmaceuticals AT-527\{SZA63631\}Biostatistics Documentation\SAP\AT-03A-001\_V1.0\_COVID SAP PA7.doc

Author: [REDACTED]

Version Number: V1.0

Version Number: V1.0

Version Date: 15 April 2021

Template No.: CS\_TP\_BS016 Revision 6

Reference: CS\_WI\_BS005

Effective Date: 02Dec2019

Copyright © 2009, 2010, 2012, 2016, 2018, 2019 [REDACTED] All rights reserved. The contents of this document are confidential and proprietary to [REDACTED] Holdings Inc. and its subsidiaries. Unauthorized use, disclosure or reproduction is strictly prohibited.

The SARS-CoV-2 test results during the study will be captured by the Central Laboratory. The date of first negative SARS-CoV-2 is defined as the earliest date when the test result is negative.

Analysis of this endpoint will be performed on the mITT analysis set only. Analyses will be carried out based on both COBAS and TaqPath results.

The following algorithm will be followed to determine how a subject which didn't meet the event (i.e., Negative SARS-CoV-2) should be censored:

1. If the subject has no post-baseline SARS-CoV-2 test results, the subject will be censored at the date of first dose of study drug;
2. If the subject's SARS-CoV-2 test remain positive during the study, the subject will be censored at the latest day of SARS-CoV-2 test date;

#### **16.2.3.6. Proportion of Subjects SARS-CoV-2 Positive at Each Time Point**

The proportion of subjects who are SARS-CoV-2 positive (i.e. detectable) at each scheduled time point will be analyzed as secondary efficacy endpoints. Analyses will be carried out based on both COBAS and TaqPath results. The SARS-CoV-2 test results will be collected by the Central Laboratory. Missing SARS-CoV-2 test results will be treated as positive.

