6. STUDY PROCEDURES AND GUIDELINES

Study-specific assessments and the study schedule are summarized in [Table 6-1](#). An "X" indicates when the assessments are to be performed.

Due to COVID-19 restrictions/policies/quarantines and to maintain safety of staff at individual sites and for individual subjects, it is acknowledged that strict adherence to [Table 6-1](#) for those procedures requiring direct contact with patients (such as laboratory sampling, physical examination, etc) may not be possible for every timepoint listed. The sites should try to maintain the schedule as closely and as safely as feasible, but temporal divergence for these direct contact procedures will not be considered a protocol deviation.

Hospital discharge may occur at any point. The date and time for the hospital discharge decision should be documented in the study records, as duration of hospitalization is a secondary study endpoint.

For subjects who are discharged before Day 14, assessments through Day 14 may be collected, either through at-home visits by trained medical professional(s), outpatient visits or by telephone follow-up, as feasible depending on the site and subject limitations.

If a subject is discharged before dosing is complete, the discharge plan should include completion of study drug dosing.

Protocol Number: AT-03A-001

Follow-up evaluations will occur at 7 days, 14 days and 49 days after study completion at nominal Day 14, according to the table below.

Additional logistical considerations and clarifications

- It is logistically feasible and acceptable for Screening and Day 1 to occur on the same day, as long as eligibility is confirmed before dosing is initiated. If the Screening and Day 1 visits are on the same day, duplicate assessments and laboratory samples do not need to be collected twice.
- Once subjects are confirmed eligible at Screening, randomization and dosing should be initiated within 24 hrs.

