a) Prior to the first dose b) Height at Screening only. c) For females of childbearing potential: serum pregnancy test at Screening. d) Collected at same time as safety lab draw. e) ET=Early Termination f) As quarantine and other factors may limit the subject's ability to return to the clinic, the follow-up assessments may be conducted by telephone, video platform or at-home visits by trained medical professional(s) (with a ± 2 day window). If this follow-up is done by telemedicine, no SARS-CoV-2 samples will be collected. g) Optional h) See [Section 6.9](#) for details of assessments, including ordinal scales for overall Clinical Status and Respiratory Support. i) Not necessary if subject already discharged from hospital j) After discharge, cardiac ECG parameters will be collected on outpatients. k) After discharge, pulse oximetry to be done on Days 2-6,8,10,12, and 14, or more frequently as needed if SpO2 < 93% l) Chest imaging (chest x-ray, CT scan, etc.) will be obtained ideally at Screening but can occur within 48 hours before screening as long as the clinical status of the subject has not changed, in the opinion of the investigator. m) Dosing on Day 1 can occur at any time of day (AM or PM). n) Collect prior to the 3rd dose (on Day 2). o) Collect prior to the 5th dose (on Day 3).

Protocol Number: AT-03A-001

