6.6. COVID-Specific Tests

Diagnostics and SOC treatment of COVID-19 are constantly evolving. The current protocol targets capture of COVID-specific parameters known to be important or potentially important at this time:

- SARS-CoV-2 qualitative testing. At Screen, subjects will typically have been identified as presumptively SARS-CoV-2 infected. The initial local SARS-CoV-2 test result will be confirmed at Screening by one of the FDA-EUA assays. The FDA-EUA assay will be used to assess SARS-CoV-2 viral presence in nasopharyngeal (preferentially) or throat swabs at periodic timepoints in this study, as indicated in [Table 6-1](#). As this may be a relatively uncomfortable procedure for some subjects, and such sampling is biohazardous for caregivers, it is acknowledged that some subjects may not be able to provide samples for all timepoints listed. Although sampling should be encouraged at all timepoints listed through Day 14, key SARS-CoV-2 testing assessments are at Screening, Day 5 and Day 14. Sampling during follow-up is supplemental, to be collected as feasible, considering those visits are likely to be conducted via telemedicine.
- Residual eluates (in solution) from nasopharyngeal or throat swabs obtained for SARS-CoV-2 may be stored frozen for eventual quantitative testing, possible resistance analyses, and viral infectivity assays if the additional handling and storage do not impose undue exposure biohazards for site staff and the central laboratory.
- Serologic D-dimer levels, a reflector of a potential hyper-coagulopathy that is common in COVID-19 patients, for future exploratory analyses. Note: If the site uses D-dimer levels for patient management, separate D-dimer levels can be obtained locally as available, at investigator preference per their local standard of care.
- Stored serum or plasma samples will be collected for possible eventual analyses of various cytokines (including interleukin-6), antibody to SARS-CoV-2, other relevant COVID-specific tests (e.g. C-reactive protein) or SARS-CoV-2 tests (e.g. antibody tests), as reliable validated assays become available.

Protocol Number: AT-03A-001

Note: In an effort to standardize the method for collection of nasopharyngeal samples during the study, the same nostril in an individual subject should be used (if possible) if only one nostril will be sampled.

The sampling schedule for the above tests is specified in [Table 6-1](#).

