**Table B: Analysis Visit Windows**

Scheduled Visit	Target Day of the Visit	Analysis Visit Window
Analysis visit windows for safety labs and SARS-CoV-2 Test		
Baseline	Day 1	Day -1 or Day 1/before 1 st dose
Day 2	Day 2	Day 2 to Day 3
Day 5	Day 5	Day 4 to Day 6
Day 8	Day 8	Day 7 to Day 9
Day 10	Day 10	Day 10 to Day 11
Day 12	Day 12	Day 12 to Day 13
Day 14	Day 14	Day 14 to Day 18
Day 21	Day 21	Day 19 to Day 25
Day 28	Day 28	Day 26 to Day 46
Day 63	Day 63	Day 47 to Day 79

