## 16.2. SECONDARY EFFICACY

### 16.2.1. KEY SECONDARY EFFICACY ENDPOINTS

#### 16.2.1.1. Change from Baseline in Quantitative SARS-CoV-2

The first key secondary endpoint is the change from baseline in amount of quantitative SARS-CoV-2 as measured by RT-PCR at the time points required in the protocol schedule of assessments (Days 2, 5, and 14). Quantitative SARS-CoV-2 will be assessed quantitatively via the TaqPath assay, and qualitatively via a separate assay, COBAS.

Analysis will be performed on the mITT analysis set only.

#### 16.2.1.2. Time to Clinical Recovery (days) by Day 14

The second key secondary endpoint is time to clinical recovery in days on or before Day 14, defined as

- Time to clinical recovery by Day 14 (days) = (Date of clinical recovery on or before Day 14 – Date of randomization) +1

Clinical recovery is defined as achieving the NIAID clinical status of level 6 or above, which include subjects who are no longer hospitalized (level 7 or 8) or hospitalized but not requiring supplemental oxygen (level 6). The clinical status and assessment date/time will be reported on the Ordinal Scale for Clinical Severity page of the eCRF.

The date of clinical recovery is based on the date the score is first  $\geq 6$ . Should there be no clinical recovery, then the time to clinical recovery is set to 15 days.

The 8 levels of NIAID are the following:

1. Death
2. Hospitalized, on invasive mechanical ventilation or ECMO
3. Hospitalized, on non-invasive ventilation or high flow oxygen devices
4. Hospitalized, requiring supplemental oxygen

Document: \\[REDACTED]\net\enterprise\Apps\sasdata\SASb\SAS\Atea\_Pharmaceuticals\AT-

527\SAZ63631\Biostatistics\Documentation\SAP\AT-03A-001\_V1.0\_COVID\_SAP\_PA7.doc

Author: [REDACTED]

Version Number: V1.0

Version Date: 15Apr2021

Template No.: CS\_TP\_BS016 Revision 6

Reference: CS\_WI\_BS005

Effective Date: 02Dec2019

Copyright © 2009, 2010, 2012, 2016, 2018, 2019 [REDACTED] All rights reserved. The contents of this document are confidential and proprietary to [REDACTED] Holdings Inc. and its subsidiaries. Unauthorized use, disclosure or reproduction is strictly prohibited.

5. Hospitalized, not requiring supplemental oxygen – requiring ongoing medical care (COVID-19 related or otherwise)
6. Hospitalized, not requiring supplemental oxygen – no longer requires close medical care for COVID-19  

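### Counting every missing swab as positive makes the Day 21, 28 and 63 SARS-CoV-2 positive rates mainly a count of swabs not taken

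*SAP*

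**What the plan says.** SAP Section 16.2.3.6 says that the proportion of positive subjects "at each scheduled time point will be analyzed as secondary efficacy endpoints", and then: "Missing SARS-CoV-2 test results will be treated as positive". It makes no exception for optional swabs, telemedicine visits or discharge.

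SAP Table B, under the line "Analysis visit windows for safety labs and SARS-CoV-2 Test", lists Baseline and Days 2, 5, 8, 10, 12, 14, 21, 28 and 63. SAP Section 16.2.5 compares the rates between arms at each time point with a CMH test controlling for region, and repeats this in four subsets defined by baseline viral load.

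The sampling rules are mostly in the protocol:

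- Table 6-1 marks the follow-up swabs as optional, and footnote f adds: "If this follow-up is done by telemedicine, no SARS-CoV-2 samples will be collected".
- Section 6.6 says: "Sampling during follow-up is supplemental, to be collected as feasible, considering those visits are likely to be conducted via telemedicine". For swabs generally, "it is acknowledged that some subjects may not be able to provide samples for all timepoints listed".
- Section 6 allows assessments of subjects discharged before Day 14 to be collected "either through at-home visits by trained medical professional(s), outpatient visits or by telephone follow-up".
- Section 8.2.3 defines the endpoint at Days 5 and 14, with later time points only where results exist.

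The SAP itself notes, in Section 16.2.3.4, that the test is not required after Day 14.

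**The concern.** Treating a missing result as a failure is a reasonable convention when a result was due and few are absent. After Day 14 neither condition holds. The swab is optional, the expected mode of contact is telemedicine, and telemedicine yields no sample. Most missing results would then reflect how the visit was held and say nothing about the subject's virus, yet each would enter the table and the CMH test as a positive.

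At stake is a secondary efficacy endpoint. Its follow-up rates would be pushed upwards in both arms. Any true difference would be compressed, and a difference between arms in the share of missing swabs would appear as a difference in viral clearance.

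The rule also sits awkwardly beside the SAP's other virology analyses. Section 16.2.4.1 does not impute missing viral load, and Sections 16.2.3.4 and 16.2.3.5 censor. On a natural reading, a subject negative at Days 10 and 12 with no Day 14 swab is a sustained clearance under Section 16.2.3.4 and a positive at Day 14 under Section 16.2.3.6.

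**Working it through.** The documents give no expected rate, power or missing-swab rate for this endpoint, so there is no stated figure to reproduce. Every missing share below is an assumption.

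**Formula.** Let m be the share of subjects with no swab at a visit and p the true positive share, with swabs missing independently of viral status. Under the SAP rule the reported rate is

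r = m + (1 − m)p.

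Whether or not that independence holds, r can never be below m.

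**Follow-up visits, both arms alike.**

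| m (assumed) | r if p = 0% | r if p = 5% | r if p = 10% |
|---|---|---|---|
| 50% | 50% | 52.5% | 55% |
| 70% | 70% | 71.5% | 73% |
| 90% | 90% | 90.5% | 91% |

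At m = 90%, moving the true rate from 0% to 10% moves the reported rate by one point.

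**Follow-up visits, arms differing only in missing swabs.** Take p = 5% in both arms, with m = 50% in one and 30% in the other:

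- 0.50 + 0.50 × 0.05 = 0.525
- 0.30 + 0.70 × 0.05 = 0.335

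The apparent difference is 19 points where the true difference is zero. With 40 per arm (81 randomised in Part A, about half in each arm), a two-sided 5% test of two proportions would reject about 40% of the time: the pooled rate is 0.43, the null standard error is √(2 × 0.43 × 0.57/40) = 0.111, the standard error under these rates is 0.109, and (0.19 − 1.96 × 0.111)/0.109 ≈ −0.25.

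**Day 14, for scale only.** Protocol Section 1.1 reports that about 47% on AT-527 and 22% on placebo had no detectable RNA at Day 14, in the interim subset with baseline viral load at or above the median. So 53% and 78% were still detectable, a gap of 25 points. With equal missingness the gap shrinks by the factor (1 − m):

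| m in both arms (assumed) | AT-527 | Placebo | Gap |
|---|---|---|---|
| 0% | 53% | 78% | 25 points |
| 25% | 64.75% | 83.5% | 18.75 points |
| 50% | 76.5% | 89% | 12.5 points |
| 75% | 88.25% | 94.5% | 6.25 points |

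With unequal missingness the gap vanishes when the AT-527 share reaches (0.78 − 0.53)/0.47 = 53% with none missing on placebo, or (0.835 − 0.53)/0.47 = 65% with 25% missing on placebo. More missing swabs on placebo than on AT-527 could instead widen the gap. Nothing in the documents says which of these applies.

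**The case against.** **The output was dropped.** The changes form of 16 March 2022 lists this proportion among the items not presented, so no reported result rests on the rule. This stands and limits the impact. But the form's context is early termination, it does not correct the rule, and it says that the SAP will not be updated.

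**The endpoint's main days are 5 and 14.** Protocol Sections 2 and 8.2.3 and the SAP's secondary objectives name those days, and Protocol Section 6.6 calls them key. Missing as positive is a familiar conservative convention there. This also stands, and it is why the point is confined to the other visits, above all those after Day 14.

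**Discharge bias through Day 14.** A reader might infer that the rule turns recovered, discharged subjects into positives and so works against a drug that speeds recovery. The documents do not support going that far:

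- Discharge is not viral clearance. In the interim subset 53% and 78% were still detectable at Day 14, so many unswabbed subjects could truly be positive.
- Home and outpatient visits are allowed alongside telephone contact. Apart from Day 1, the optional footnote marks only the early termination and follow-up swabs.
- No missing-swab or discharge rates by arm are given.

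**Observed cases are no cure through Day 14.** Suppose true positivity is 60% vs 45%, 20% vs 35% of swabs are missing, and every missing subject is truly negative (all assumed). The SAP rule gives 0.20 + 0.60 = 80% vs 0.35 + 0.45 = 80%. Observed cases give 0.60/0.80 = 75% vs 0.45/0.65 = 69%, about 6 of the true 15 points. Both are biased. At Days 5 and 14 the choice is a trade-off, which calls for a sensitivity analysis rather than replacement of the rule.

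**Conclusion.** For the Day 21, 28 and 63 visits the rule is wrong as written. It counts as positive subjects whom the plan does not require to be tested, and it contradicts the protocol's wording for later time points. The reported rate is at least the share of missing swabs. That follows from the rule alone; only the illustrative 50% to 90% shares are assumed. The protocol's expectation of telemedicine makes a large share likely but gives no figure.

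Through Day 14 the conclusion is weaker. Some attenuation is certain if swabs are missing equally and independently of viral status. Otherwise the size and direction of any bias depend on rates that the documents do not give. Nor can one conclude that a reported trial result is biased. The endpoint is an other secondary with nominal p-values only (SAP Section 7.4), it lies outside the gatekeeping sequence, and the output was not presented. Practical impact is low.

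**What to change.** Amend SAP Section 16.2.3.6 as follows, and carry the same wording into the CMH analyses of Section 16.2.5:

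- Apply missing as positive only to the Day 5 and Day 14 analyses, and add an observed-case or multiple-imputation sensitivity analysis at those days.
- At all other visits, and always after Day 14, report the proportion positive among subjects tested, with no imputation.
- Show the number tested per arm at every visit. A footnote should say that those tested after Day 14 are a selected group.

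The cost is a few lines of SAP text and one extra table; no new data are needed. Since the 2022 form says that the SAP will not be updated, the minimum is to attach this correction to the endpoint definition before anyone tabulates it later.
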